### ***Undermining Cessation***

We emphasize that this is not a cessation trial, though we will collect various cessation outcomes. Nonetheless, it is possible that use of e-cigarettes will undermine quitting (though this would be contrary to existing literature). At the end of the study, participants will be advised to stop using all tobacco products, including e-cigarettes.

### ***Diversion of e-cigarettes***

We will strongly advise participants that they are not to share the study product with others, and that they should store the product in a secure area that is out of reach of children and pets. We cannot directly assess any diversion/uptake from the perspective of adolescents, since that would require separate consent, and is a separate research question.

### ***Confidentiality***

We will use the participant's name only on the screening and informed consent documents and these will be kept in a locked file, to be kept centrally at our study office, or electronically in Redcap. Copies of informed consent will be kept by research personnel under lock and key, or on recap when collected electronically. When consent is collected electronically, our study team has a combination laptop/tablet that will be used for the eProcess. No information will be stored locally on the laptop/tablet; all information will be stored securely in REDCap if captured electronically. The HIPAA form can be signed on paper or electronically. For the electronic process, all pages of the approved HIPAA document will be uploaded into REDCap, using a SCTR-developed template and procedures, for review by the participant. Instead of signing on paper, a participant will enter his/her name, date, and sign electronically (with mouse or finger) in REDCap. Each participant will still receive a paper copy of the "Notice of Privacy Practices" and each signed HIPAA can be downloaded from REDCap as a PDF. These procedures will be done on our research team's combination laptop/tablet, but no data will be stored on the laptop/tablet; all data will be stored securely in REDCap.

The research materials will become part of the modern record keeping facility of the Institute of Psychiatry, which will minimize risks to the privacy of participants. All interviews, records, charts, rating scales, and other patient information will be kept in locked files at the Cancer Control Program, with limited access to the study personnel. All database files will include password protection to further ensure confidentiality.

### **3. Potential Benefits of the Proposed Research to the Participants and Others**

This study is not likely to offer any direct benefit to the participants in the study.

### **4. Importance of the Knowledge to be Gained**

In an ever-changing marketplace of tobacco-produces and nicotine-delivery devices, e-cigarettes are arguably the most popular new products available to smokers. The most important question about e-cigarettes is whether it will have a positive or negative impact on public health. The impact on public health is largely dependent on whether e-cigarettes reduce combustible cigarette use. This study will provide information about whether one e-liquid characteristic will impact reinforcement value of e-cigarettes among current combustible cigarette users.

## Statistical Analysis Plan

Power analysis was completed for the primary outcome of percentage reduction in average cigarettes per day smoked in the last week of sampling, and based on data from [name] previous e-cigarette sampling trial during which participants received a low power (1st Gen) device with one of two nicotine concentrations (low or high) (84). We hypothesize that the impact of nicotine concentration on CPD reduction would be similar here for the low power groups and that the effect would reversed, but of similar size, in the high-power groups. In this case, a sample size of 40 participants / group will provide 80% power to detect an interaction among the two factors with a 0.050 significance level, assuming that the common standard deviation is 38% reduction in CPD, as was the case in [name] trial (84). However, we inflate this sample size by 10%, accounting for attrition over time, and thus aim to **recruit 45 participants randomized per group (total N=180)**.

For aims 1 and 2, we will assess the impact of concentration and power on each outcome across time using a generalized estimating equation that includes concentration, power, sampling week (time), and their interactions. Hypothesis 1 will focus on percentage reduction in CPD, Hypothesis 2 will focus on e-cigarette uptake (puffs per day), and Hypothesis 3 will focus on complementary measures of preference/demand, all of which are captured at Visit 4. Outcomes that are skewed (e.g., demand parameters, urinary cotinine) will be log transformed. It is possible that reductions in CPD will be bimodal in the last week of sampling, reflecting a subset of participants who may quit smoking during the trial. In this case, we would conduct a Chi-square test on the proportion of participants who reduce their smoking by at least 50%. Exploratory analyses on age will be conducted by adding age to the model. As described in the Career Development Plan, [name] (co-mentor) will be meeting with [name] monthly for training in these analyses, and will also be available to assist with any unexpected issues. Gender will be examined separately as a direct or moderating influence on all outcomes.

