**Specific Aim 1:** To understand the impact of nicotine concentration and device power on cigarette smoking (cigarettes smoked per day; CPD) and smoke exposure (expired breath carbon monoxide; CO). Hyp1: There will be an interaction such that a higher (vs. lower) nicotine concentration will produce greater reductions in CPD and CO when device power is low, and a lower nicotine concentration will produce greater reductions in CPD and CO when device power is high. Hyp2: Parallel analyses will test the main and interactive effects of nicotine concentration and device power on e-cigarette use (hypothesizing more puffs per day).

**Specific Aim 2:** To understand the impact of nicotine concentration and device power on relative reinforcement value (choices to smoke versus use an e-cigarette in a lab-based preference task, demand for each product on a hypothetical purchase task). Hyp3: There will be a similar interaction such that a higher nicotine concentration will result in fewer choices to smoke a low power device, and a lower nicotine concentration will result in fewer choices to smoke in a high-power device.

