Because nicotine delivery and sensorimotor characteristics are a joint function of e-liquid and device characteristics, smokers may choose products that produce the optimal nicotine delivery and sensorimotor stimulation. Thus, we expect (hypothesize) an interaction between concentration and power, and this becomes our **core scientific premise**. A higher-powered device that can deliver greater nicotine per puff of aerosol is likely to be more reinforcing when it is paired with a low nicotine concentration because this combination produces the optimal level of nicotine delivery. Low nicotine concentrations paired with low power may not deliver enough nicotine or provide enough sensorimotor stimulation to be reinforcing, while high nicotine concentrations paired with high power may provide aversive levels of nicotine or an aversive throat hit. Consistent with this prediction, a small study of 20 e-cigarette users found that users of higher powered devices used lower e-liquid nicotine concentrations than users of lower-powered devices, but obtained higher levels of plasma nicotine. Furthermore, a recent survey of 436 current e-cigarette users found a strong negative relationship between the power of device settings and user's chosen e-liquid nicotine concentration ( $r = -0.44$ ). In one experimental lab study, smokers reported that a lower concentration was required to produce the optimal throat hit when using a higher power setting. However, we also know that e-cigarette users can compensate for changes in these characteristics by modifying their puffing behavior. When device power or nicotine concentration are lower, e-cigarette users have been shown to take longer puffs, more puffs, and ultimately consume more e-liquid. Thus, an alternative hypothesis is that these characteristics may be relatively unimportant, as long as users are able to modify their behavior in order to achieve the desired effect. The interactive effects of concentration and power remain unclear, and serve as the central focus of this application.

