### C8. Statistical Considerations:

Power analysis was completed for the primary outcome of percentage reduction in average cigarettes per day smoked in the last week of sampling, and based on data from [name] previous e-cigarette sampling trial during which participants received a low power (1st Gen) device with one of two nicotine concentrations (low or high). We hypothesize that the impact of nicotine concentration on CPD reduction would be similar here for the low power groups and that the effect would be reversed, but of similar size, in the high-power groups (Figure 3a). The hypothesized interaction is shown during the last week of sampling for simplicity in Figure 3b, specifically that for the low power setting, a higher concentration will produce a larger decrease in cigarettes per day than the low concentration, but for the high-power setting, a higher concentration will produce a smaller decrease in cigarettes per day than the low concentration. We use the methods described by Fleiss for estimating power for interaction effects. As he notes, the variance of an interaction effect is four times that of the corresponding main effect. Thus, even large effects require large sample sizes to yield adequate power. In this case, a sample size of 40 participants / group will provide 80% power to detect an interaction among the two factors with a 0.050 significance level, assuming that the common standard deviation is 38% reduction in CPD, as was the case in [name] trial. However, we inflate this sample size by 10%, accounting for attrition over time, and thus aim to **recruit 45 participants randomized per group (total N=180)**.

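### Does Hypothesis 1 need pre-specified concentration contrasts at 20 W and at 40 W in addition to the interaction test?

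*Combined protocol and SAP*

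**What the plan says.** Hypothesis 1, in Specific Aims, is framed as an interaction and then describes its shape. For the 20 W groups it predicts that "a higher (vs. lower) nicotine concentration will produce greater reductions in CPD and CO when device power is low". For the 40 W groups the expected direction is the opposite one: "a lower nicotine concentration will produce greater reductions in CPD and CO when device power is high".

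The Statistical Analysis Plan sizes the trial on one outcome: "Power analysis was completed for the primary outcome of percentage reduction in average cigarettes per day smoked in the last week of sampling". It takes the concentration effect at low power from an earlier sampling trial and assumes that at high power "the effect would reversed, but of similar size, in the high-power groups". Section C8 states that "a sample size of 40 participants / group will provide 80% power to detect an interaction among the two factors", with an SD of 38 points and a 0.050 significance level. The number is then raised to 45 per group.

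The analysis sentence, essentially the same in C8 and in the SAP, models each outcome "across time using a generalized estimating equation that includes concentration, power, sampling week (time), and their interactions". A fallback is given in case the outcome has two peaks: "It is possible that reductions in CPD will be bimodal in the last week of sampling". It then compares the proportions with at least a 50% reduction.

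Neither section names a 3 versus 12 mg/ml comparison within 20 W or within 40 W, and neither says in words which term of the model answers Hypothesis 1.

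**The concern.** The interaction depends only on the difference between two concentration effects. A large effect at 20 W with none at 40 W can give the same interaction as equal and opposite effects. Those are different answers to Hypothesis 1: one says the lower concentration is better at 40 W, the other says concentration does not matter there. The interaction p-value cannot separate them. The main effect of concentration does not help either, because it averages over power and is near zero under the predicted crossover.

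At stake is the trial's central claim. Section A2 itself raises a rival view, that "an alternative hypothesis is that these characteristics may be relatively unimportant". The interaction test bears on that view, but not on whether the direction changes. If a report relied on a significant interaction and means of opposite sign, it could announce a reversal that is not there.

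**Working it through.** **Inputs.** SD 38 points, 40 per group, 80% power and significance level 0.05 (SAP and C8); 45 per group after inflation (same places). The effect size is not given in the text, and the figure showing it was not available for this check, so it is back-solved. Two-sided testing is assumed. A positive effect means 12 mg/ml reduces smoking more than 3 mg/ml.

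**The plan's own figures.**
- Attrition: 40 / 0.9 = 44.4, rounded up to 45, as stated.
- SE of the interaction (a difference of two differences): 38 × √(4/40) = 12.02. C8 says its variance is four times that of a main effect: 38² × 2/80 = 36.1, and 4 × 36.1 = 144.4 = 12.02². This agrees.
- Interaction detectable with 80% power: (1.960 + 0.842) × 12.02 = 33.7 points, or ±16.8 if split equally as the plan assumes.

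The 80% cannot be confirmed without the effect size, but it is coherent and is not disputed.

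**Precision within one power level.**

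| | 40 per group | 45 per group |
|---|---|---|
| SE = 38 × √(2/n) | 8.50 | 8.01 |
| 95% half-width = 1.96 × SE | 16.7 | 15.7 |
| Power for a 16.8-point effect | 51% | 56% |
| Power for both effects (product) | 26% | 31% |

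**How often a false reversal would appear.** Independent normal estimates at 20 W and 40 W were simulated, each with SE 8.50 (4,000,000 draws).

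| True effect at 20 W, 40 W | Interaction significant | Significant, with opposite signs as predicted | 40 W interval wholly on the reversal side |
|---|---|---|---|
| 16.8, −16.8 | 80% | 79% | 51% |
| 16.8, 0 | 29% | 25% | 2.5% |
| 33.7, 0 | 80% | 48% | 2.5% |

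In the second row, 0.247 / 0.289 = 86% of significant results look like a reversal by sign. However, the interaction is significant with a 40 W interval that includes zero in 0.265 of trials, so in only 0.289 − 0.265 = 0.024 does the interval exclude zero. Hence (0.247 − 0.024) / 0.247, about nine in ten of the false-looking reversals, would have a 40 W interval that includes zero. Reporting the estimate with its interval is enough to prevent the error.

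**What the planned model supplies.** With both factors, week and all their interactions in the model, each cell mean at each week is estimated. The concentration effect at 20 W or 40 W in the last week is a linear combination of fitted terms, so no new term, data or participant is involved. The primary-outcome definition and the fallback both refer to the last week, which settles which week to use.

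**The case for a change.** The strongest case for a change is that the central hypothesis states a direction at each power level, no within-power estimate is promised, and closing the gap would cost a few sentences and two contrasts. Naming the comparison, the week and the standard for claiming a reversal before the data are seen also removes discretion. The numbers give this some force: with a 16.8-point effect at 20 W and nothing at 40 W, most significant interactions would look like a crossover by sign alone.

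The factual part stands: the comparison is not named. The harm does not follow from the plan. It needs a report that infers a reversal from the p-value and the signs while leaving out intervals the model provides, and neither C8 nor the SAP describes such an inference. The all-trials figure on the plan's own anchor is 25%; the 48% needs a 20 W effect twice that anchor.

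The gain is also limited. Under a true equal reversal, 31% of all trials would have a significant interaction with a 40 W interval that includes zero. A written rule would often leave the question open, and the planned test and the sample size would be the same with or without it.

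**Conclusion.** No change is called for. The plan tests and powers the interaction that Hypothesis 1 names, and following it as written gives a sound answer to that question. The missing within-power contrasts, and the unstated choice of the last week, are details a competent analyst supplies from the planned model. When the results are read, a claim of reversal should rest on the two estimates and their intervals. An inconclusive 40 W interval (half-width 16.7 points at 40 per group, 15.7 at 45) should not be taken as evidence against one, since power for each effect is only about 51% to 56%, and 26% to 31% for both.

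These figures rest on the back-solved 33.7-point contrast, an equal split between power levels, two-sided testing at 0.05 and a normal approximation. The conclusion does not depend on them: it follows from the hypothesis being stated as an interaction and from the model containing what is needed to describe its shape.

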### C3. Participants:

Daily cigarette smokers (n=200) will be recruited from the local community using standard media outlets. We will also submit a Research Data Request to obtain a recruitment report of MUSC patients who potentially meet eligibility criteria. The study team will not cold-contact any patients who have opted out of receiving contact about research or who have met the maximum number of contact attempts at the time of recruitment. We will reach out to these potential participants via MyChart message, text message, phone call, or email no more than three times via any one contact method. Although we anticipate having 180 participants complete the study, here we have increased this sample size to 200 in anticipation of attrition. We will recruit an equal number of young adult (21-30) and older adult smokers (>30) to allow for exploratory analysis on the impact of age. In/exclusion criteria are designed to enroll relatively healthy smokers who predominately use cigarettes and have limited experience with e-cigarettes. Inclusion criteria include a) adults who have been smoking at least five cigarettes daily for the past year (baseline CO > 8ppm), b) rate their interest in using e-cigarettes as >5 on a 0-10 scale, c) have a smartphone that can receive text messages and has access to the internet or has an e-mail account they check daily and d) must be age 21 or older. Exclusion criteria include a) use of tobacco products other than cigarettes, including e-cigarettes, on ten or more days in the past 30 days, b) current use of cessation medications, c) pregnant, trying to become pregnant, or breastfeeding, d) recent history of cardiovascular distress in the last three months (e.g., arrhythmia, heart attack, stroke, uncontrolled hypertension), e) history of a seizure disorder, f) household member currently enrolled in the study.

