##### 1.2 Study Procedures, Materials, and Potential Risks:

###### Study Procedures:

Participants will be screened over the phone to determine initial eligibility. Alternatively, participants may complete a redcap survey to determine initial eligibility. Participants will see a script that briefly explains the study. Once participants have been determined to be initially eligible, they will be invited to participate in the consent process. The consent process will take place via one of the following modalities: 1) Remote electronic

[figure not shown]

Figure 3a: Hypothetical Changes in CPD over sampling

[figure not shown]

Figure 3b: Impact on reduction in CPD

consent (e-consent) via REDCap facilitated with a discussion over the phone, 2) Remote consent via doxy.me, or 3) in-person consent (in-person visit at start of Visit 1). During the COVID-19 restrictions, all consenting will be done remotely (not in-person). We have built in the option for electronic consent to reduce the length of the first in-person visit and while still providing ample time for the consent process. Consented participants will be asked to attend an in-person screening session. Participants will be asked to provide a carbon monoxide sample to confirm smoking status, and women will provide a urine sample for pregnancy testing. Participants will then complete a series of interview-administered and participant-administered questionnaires that assess brief medical history, tobacco use history including prior and current e-cigarette and cigarette use, current use of smoking cessation products, and demographics. After all questionnaires have been completed, study staff will determine participant eligibility.

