Participants who are eligible will then provide a urine sample for cotinine analysis and complete additional baseline questionnaires including measures of nicotine dependence. Participants will be randomized to one of four groups as described above and will have the opportunity to sample their usual brand cigarette and their assigned e-cigarette and e-liquid for the first time. After sampling each product, participants will complete additional questionnaires and complete the preference assessment where they choose between their cigarette and assigned e-cigarette. At the end of Visit 1, participants will receive a one week supply of e-liquid to take home with their assigned e-cigarette, will be enrolled in the daily electronic diary system, and will be provided with instructions for completing diaries.

Participants will return to the lab for three additional weekly visits, and will receive a new supply of e-liquid for each week. At each visit, we will assess tobacco use during the prior week, participants will provide an expired breath carbon monoxide sample, adverse events will be assessed, and participants will complete questionnaires about their assigned e-cigarette and e-liquid. At the fourth and final weekly visit, participants will complete the sampling and preference assessment again, providing another urine sample for cotinine testing, and return any unused study product.

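### The primary model for percentage CPD reduction pre-specifies no baseline covariate, so the powered interaction test may forgo some precision at almost no cost to recover

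*Combined protocol and SAP*

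**What the plan says.** The Statistical Analysis Plan and section C8 give the same model for every outcome under both aims: "a generalized estimating equation that includes concentration, power, sampling week (time), and their interactions". The trial is sized on the "primary outcome of percentage reduction in average cigarettes per day smoked in the last week of sampling". Baseline CPD therefore enters the primary analysis only as the denominator of that percentage.

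Three kinds of baseline information are available before assignment:

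- **Smoking.** Section 1.2 (Study Procedures) has screening questionnaires that cover "tobacco use history including prior and current e-cigarette and cigarette use".
- **Dependence.** The same section has eligible participants "complete additional baseline questionnaires including measures of nicotine dependence" and describes this step before randomization. Section C7b lists the instruments: FTND, WISDM and the Penn State scales.
- **Age.** Section C3 says "We will recruit an equal number of young adult (21-30) and older adult smokers (>30", and gives exploratory analysis of age as the reason.

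Section A4 names age and dependence among the characteristics likely to affect relative reinforcement value, and assigns them to exploratory tests. The SAP adds age to the model in exploratory analyses only and examines gender separately. Section C1 allows flavor choice as a covariate if needed, without a criterion.

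**The concern.** The study is sized at 80% power for one interaction contrast, and section C8 itself notes that an interaction has four times the variance of a main effect. A main-effect covariate measured before randomization leaves the question unchanged and removes whatever residual variance it explains. The plan records such variables and expects two of them to matter, yet leaves all of them out of the powered test.

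Dividing by baseline CPD is not the same as adjusting for it, and it uses no information on dependence or age. Leaving adjustment to exploratory analyses has a second, smaller drawback: without a fixed list, the choice of which adjusted result to show is made after the data are seen.

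**Working it through.** **Inputs from the SAP.** For size and power, the plan says "a sample size of 40 participants / group will provide 80% power to detect an interaction among the two factors". The test is at the 5% level; sidedness is not stated, and I take two-sided. The SD is 38 percentage points, taken from a previous sampling trial. The text gives no numerical effect size. Section C8 points to Figure 3, which I could not see. So 40 per group can be back-solved but not independently confirmed. Like the plan's own sizing, the calculation treats the last sampling week as a single comparison.

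**Attrition step.** 40 / 0.9 = 44.4, rounded up to 45 per group, or 180 in total. This agrees with the plan.

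**Implied contrast.** The interaction is a difference of differences over four cells.

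- SE = SD × √(4/n) = 38 × √(4/40) = 12.02 points.
- Contrast for 80% power = (1.960 + 0.842) × 12.02 = 33.7 points, that is, opposite simple effects of about 16.8 points each.

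**Effect of covariates.** If baseline covariates explain a share R² of the outcome variance, the SE becomes 12.02 × √(1 − R²). Holding the contrast at 33.7, power = Φ(33.7/SE − 1.96). The documents give no R²; the values below are an assumed range.

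| R² (assumed) | SE | Power at 40 per cell | n per cell for 80% power |
|---|---|---|---|
| 0 | 12.02 | 80.0% | 40 |
| 0.05 | 11.71 | 82.0% | 38 |
| 0.10 | 11.40 | 84.0% | 36 |
| 0.20 | 10.75 | 87.9% | 32 |

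The last column is 40 × (1 − R²). It shows what the precision would be worth and is not a proposal to recruit fewer.

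**Cost if the covariates explain nothing.** With 160 analysed and four cells there are 156 residual degrees of freedom. Losing three of them costs less than 0.1 point of power. Chance imbalance in three covariates inflates the variance by roughly 155/152 = 1.020. The ratio of contrast to SE then falls from 2.802 to 2.802/√1.020 = 2.774, and power to Φ(2.774 − 1.960) = 79.2%, a loss of about 0.8 point. Break-even is at R² = 1 − 152/155, about 2%. The same allowance lowers the last three powers in the table to about 81.2%, 83.3% and 87.3%.

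**Which covariate would help.** Baseline CPD alone may add little, because the outcome already divides by it. The documents contain nothing from which to apportion the gain among CPD, dependence and age.

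**The case against.** The strongest reply is that nothing here is an error. Under randomization the unadjusted interaction test is valid. That stands in full.

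The authors also considered these variables: A4 lists age and dependence, and the SAP adds age in exploratory models. It would therefore be wrong to infer that the plan ignores them. The disagreement is only about exploratory versus primary status.

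The gain rests wholly on an assumed R², which may be close to zero. That stands too, and is why the result is given as a range that includes zero. A reader might infer that dependence and age would supply most of the gain. No passage says that either predicts CPD reduction, so this is not supported.

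A reader might also infer that the age quota obliges the analysis to adjust for age group. Section C3 describes a recruitment quota; no stratified randomization is described, so adjustment would serve precision, not validity.

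The margin may be wider than 80%. Section C3 expects 180 completers from 200 recruited, whereas C8 and the SAP randomize 180. On the C3 reading, 45 per cell give SE = 38 × √(4/45) = 11.33 and power Φ(33.7/11.33 − 1.96), about 84% without adjustment. That weakens the urgency but does not remove the benefit.

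Finally, the covariates need definitions that the plan lacks. C7b lists several dependence instruments. Nothing I could read fixes the source and window of baseline CPD; the daily diary starts only at Visit 1, and the Table 1 columns for timeline followback were not legible in my text. This adds to the drafting but is not a reason against the change.

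**Conclusion.** The point holds as an optional efficiency improvement. The primary model carries no pre-randomization covariate, the candidates are already collected, and the plan itself regards two of them as likely influences. At the planned SD and 40 per cell, power would rise from 80% to about 82%, 84% or 88% if the covariates explained 5%, 10% or 20% of the variance. The possible loss is under about 1 point if they explain nothing.

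This rests on the assumed R² values, a two-sided test and a contrast back-solved from the stated power. It does not show that the stated sample size is wrong, that the 80% figure is wrong, or that the unadjusted result would be biased; the documents support none of those readings.

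**What to change.** Before any unblinded analysis, add to the SAP that the primary GEE includes these main-effect covariates:

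- log baseline CPD, using the same pre-randomization value that forms the denominator of the percentage reduction, with its source and window stated;
- one named cigarette dependence score from Visit 1, for example the FTND;
- age group, 21-30 versus over 30.

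Report the model without covariates as a sensitivity analysis. Leave the sample size and the exploratory moderation analyses as they are. The Chi-square fallback for a bimodal outcome is not affected by this change.

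The cost is a short SAP amendment, including the baseline CPD definition that the primary outcome needs in any case. It requires no new data, procedure or participant burden.
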